## 9.6. STUDY DRUG EXPOSURE

The following exposure information will be summarized based on the SAF using descriptive statistics as well as counts and percentages, as appropriate, depending on the study period:

- **Across all periods overall and by Pre-randomization Group:** average of total nightly dose of JZP-258 (in g/night) and duration of exposure to JZP-258 (in days);
- **OTTP overall and by Pre-randomization Group:** total nightly starting dose of JZP-258 (in g/night), total nightly stable dose of JZP-258 (in g/night), average of total nightly dose of JZP-258 (in g/night), time to get to total nightly stable dose (in days), and duration of exposure (in days) regardless of the JZP-258 total nightly received dose;

- **SDP overall and by Pre-randomization Group:** average of total nightly dose of JZP-258 (in g/night) and duration of exposure (in days) regardless of the JZP-258 total nightly received dose;
- **RWP overall and by Pre-randomization Group as well as by received treatment group:** JZP-258 total nightly received dose (in g/night) and duration of exposure (in days) regardless of the JZP-258 total nightly received dose as well as by received treatment group (JZP-258 and placebo);
- **OLE overall and by Pre-randomization Group:** average of total nightly dose of JZP-258 (in g/night) and duration of exposure (in days) regardless of the JZP-258 total nightly received dose

With the following exception, interruptions, compliance, and dose changes are not considered for duration of exposure. For OLE re-entry subjects, interruptions between the end of the DB RWP and OLE Day 1 will be excluded from the duration of exposure.

Starting and stable JZP-258 total nightly doses will be summarized using descriptive statistics as well as by total nightly dose level category using counts and percentages.

Listings of study drug exposure and of the dosing diary will be presented.

### 9.6.1. DERIVATIONS

Duration of exposure to study drug, in days, will be computed as follows:

(Date of last dose of study drug administered during the study period – date of first dose of study drug administered during the study period) + 1.

For rollover subjects (i.e., subjects who rolled over into the OLE directly after completion of the DB RWP), the duration of exposure to study drug across all study periods, in days, will be computed as follows:

(Date of last dose of study drug administered during the study – date of first dose of study drug administered during the OTTP) + 1.

For OLE re-entry subjects, the duration of exposure to study drug across all study periods, in days, will be computed as follows:

[(Date of last dose of study drug administered during the Main Study – date of first dose of study drug administered during the OTTP) + 1] + [(Date of last dose of study drug administered during the OLE – date of first dose of study drug administered during OLE) + 1].

Time to get to the stable dose, in days, will be computed as follows:

(The Study Drug Administration Date of the Total Nightly Stable Dose when it was first achieved based on total dose consideration – date of the first day of the first Open-Label study drug dispensation) + 1. The stable dose determination and time to get to the stable dose will only be calculated for subjects entering the OL SDP.

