5.1.1.2 Placebo

A matching oral solution to JZP-258 will be provided. The placebo formulation is an aqueous solution consisting of sodium citrate, malic acid and sucralose. All ingredients are compendial (USP/NF).

Placebo treatment is applicable to the Double-Blind Randomized-Withdrawal Period only.

Treatments Administered 5.1.1.3

During the Optimized Treatment and Titration Periods all subjects will receive open-label JZP-258.

Pre-randomization Groups 1 and 2

Subjects entering the study on Xyrem alone or on Xyrem plus an additional anticataplectic will be switched from their current dose of Xyrem to JZP-258 on a gram to gram straight conversion at the start of the Optimized Treatment and Titration Period and remain on that dose for 2 weeks. If further titration is needed, titration will proceed at a rate of 1 or 1.5 g per night per week during this period not to exceed a total dose of 9 g per night.

Pre-randomization Groups 3 and 4

Subjects entering the study receiving treatment with a non-Xyrem anticataplectic only or not treated with any anticataplectic agent will receive an initial dose of JZP-258 4.5 g per night at the start of the Optimized Treatment and Titration Period. Dose adjustments will proceed at a rate of 1 or 1.5 g per night per week until a tolerable dose of JZP-258 is reached over a period of 2 weeks. If needed, the dose of JZP-258 may be further titrated to a stable, tolerable, and effective dose that does not exceed a total dose of 9 g per night.

Pre-randomization Groups 2 and 3 will taper anticataplectics as described in Section 3.1.

During the Stable-Dose Period subjects will receive open-label JZP-258 at the same unchanged dose that they received during the last 2 weeks of the Optimized Treatment and Titration Period.

> Confidential Page 45 of 148

All subjects will receive blinded study drug during the Double-Blind Randomized-Withdrawal Period. At the end of the Stable-Dose Period, subjects enter the Double-Blind Randomized-Withdrawal and will be randomized 1:1 to receive either JZP-258 at the dose taken during the last 2 weeks of the Stable-Dose Period or JZP-258 placebo (at a volume equivalent to the JZP-258 dose taken in the last 2 weeks of the Stable-Dose Period).

Study drug will be dispensed at clinic visits and, if applicable, at intervals specified by state or local regulations or to resolve logistical issues.

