The Safety Population will include all subjects who took at least one dose of study medication. Safety populations will also be defined for each study period (i.e., Optimized Treatment and Titration, Open-Label Stable-Dose, Double-Blind Randomized-Withdrawal, and Open-Label Extension periods) for by-period analyses. These populations will be used for safety evaluations and efficacy summaries.

The Efficacy Population will include all subjects who are randomized to JZP-258 or placebo, who received at least 1 dose of study drug during the Double-Blind Randomized-Withdrawal Period and have at least one set of post-baseline efficacy assessments. This population will be used as the main analysis population for the primary and secondary efficacy endpoints.

9.5 **Demographics and Baseline Characteristics**

Demographics and baseline characteristics will be summarized descriptively for the Safety Population, Efficacy Population, and the Safety Population from the Open-Label Extension period. For the Efficacy Population, results will be provided by randomized treatment group.

9.6 **Handling of Dropouts and Missing Data**

Subjects who drop out of the study will not be replaced. Methods of addressing missing efficacy data are described in Section 9.10.

> Confidential Page 85 of 148

Clinical Trial Protocol: 15-006 Amendment 5

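### The across-period JZP-258 exposure formulas in SAP 9.6.1 count a placebo-arm subject's double-blind placebo days (nominally 14) as exposure to JZP-258

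*SAP*

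**What the plan says.** The first bullet of SAP 9.6 lists what is summarized across all periods, overall and by Pre-randomization Group: "average of total nightly dose of JZP-258 (in g/night) and duration of exposure to JZP-258 (in days"). The quantity named is JZP-258.

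SAP 9.6.1 gives across-period formulas for two kinds of subject, both worded as exposure to study drug:

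- Rollover subjects: "Date of last dose of study drug administered during the study – date of first dose of study drug administered during the OTTP", plus 1.
- Re-entry subjects: "Date of last dose of study drug administered during the Main Study – date of first dose of study drug administered during the OTTP", plus 1, added to the corresponding OLE span.

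SAP 9.6 also states the convention that "interruptions, compliance, and dose changes are not considered for duration of exposure". There is one exception, for re-entry subjects: "interruptions between the end of the DB RWP and OLE Day 1 will be excluded from the duration of exposure".

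The separate RWP row reports "duration of exposure (in days) regardless of the JZP-258 total nightly received dose as well as by received treatment group (JZP-258 and placebo"). SAP 9.9 says that data collected while placebo-arm subjects were on placebo are left out of the across-period safety summaries. SAP 9.6 and 9.6.1 contain no such rule.

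**The concern.** The label and the formula describe different things. The row is labelled as exposure to the active drug, while the formula measures time from first to last study drug. The design puts two weeks of assigned placebo inside that time for half the randomized subjects. The SAP deducts one interval off JZP-258 (the re-entry gap after the RWP) and leaves in the one that randomization imposes.

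At stake is the reported extent of exposure. Protocol 3.1.3 says the OLE was added partly to assess longer-term safety, and SAP section 10 updates the exposure summary for the final safety analysis. The error runs in one direction only, towards more exposure than occurred. The same placebo days are dropped from the across-period safety data under SAP 9.9 but kept in the exposure summary that describes them.

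**Working it through.** **Does the span contain the placebo days?** For a rollover subject, yes on any reading. The first dose (titration) and the last dose (OLE) are both open-label JZP-258, and the RWP lies between them. For a re-entry subject the first span ends at the last Main Study dose of study drug, so the answer depends on whether that term covers placebo. Protocol 5.1.1.1 and 5.1.1.2 list study drug and placebo under separate headings. The working usage, however, includes placebo:

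- Protocol 5.1.1.3: "All subjects will receive blinded study drug during the Double-Blind Randomized-Withdrawal Period".
- Protocol 9.4, on the Efficacy Population: subjects "randomized to JZP-258 or placebo, who received at least 1 dose of study drug during the Double-Blind Randomized-Withdrawal Period".
- SAP 5.3 defines the RWP safety population by double-blind study drug, then splits it by treatment received.
- The RWP exposure row in SAP 9.6 is split into JZP-258 and placebo.

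**Inputs.** Titration 12 weeks, Stable-Dose 2, RWP 2 (SAP 3.1.1); OLE 24 weeks (SAP 3.1.2); 1:1 allocation (SAP 3.3); 65 per arm (SAP 3.4); +3-day window at Visit 16 (Protocol Appendix 1.1).

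**The plan's own figures.** 12 + 2 + 2 = 16 weeks, and 2/16 = 12.5% of Main Study time on placebo, as in Protocol 3.1.3. 16 + 24 = 40 weeks, as in the Protocol synopsis. Both reproduce.

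**Placebo-arm subject completing every period.**

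- Rollover formula: 84 + 14 + 14 + 168 = 280 days.
- Re-entry formula: (84 + 14 + 14) + 168 = 112 + 168 = 280 days, whatever the gap.
- Days on JZP-258: 84 + 14 + 168 = 266.
- Excess: 280 − 266 = 14 days; 14/266 = 5.3%.
- If Visit 16 falls 3 days late: 283 against 266; 17/266 = 6.4%.

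**Mean over both arms, 1:1, full OLE.**

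- Nominal: (280 + 266)/2 = 273; 280/273 = 1.026, or +2.6%.
- Visit 16 3 days late: (283 + 266)/2 = 274.5; 283/274.5 = 1.031, or +3.1%.

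**Total excess.** OLE entry is optional (Protocol 4.3) and the documents give no uptake figure, so I assume 50% to 100% of the 65 planned placebo subjects enter.

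- At 14 days each: 65 × 14 = 910 days if all enter, 455 if half do.
- At 17 days each: 65 × 17 = 1,105 if all enter, about 553 if half do.

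The OLE is open only to subjects who complete double-blind treatment (Protocol 3.1.2 and 4.3.1). Stopping early in the RWP therefore lowers the number affected, not the excess per subject.

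**Pooled row.** The across-period row uses the Safety Population, which also includes enrolled subjects who were never randomized. With 185 enrolled and 130 randomized, that is 55 subjects with at most 84 + 14 = 98 days each. At full OLE completion the JZP-258 total for randomized subjects is 65 × 280 + 65 × 266 = 35,490 days. Adding up to 55 × 98 = 5,390 gives 40,880. The excess is 910/40,880 = 2.2% to 910/35,490 = 2.6%.

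**The case against.** The strongest reply is that SAP 9.6.1 defines exposure to study drug, and for that quantity the spans are correct. The only slip would then be one label in SAP 9.6. It is true that relabelling removes the contradiction. But the row as specified names JZP-258, and no other across-period derivation is given for it, so the number printed under that name would be wrong.

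A second reply is that two weeks off JZP-258 is an interruption, which the gross-span convention deliberately keeps. I do not find this persuasive. Assigned placebo is not an interruption, a compliance matter or a dose change in ordinary usage, and the convention does not mention it.

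Third, the placebo exclusion in SAP 9.9 may show what the programmers intend, and the table shells mentioned in SAP section 8 may settle it. The shells are not in the documents. The SAP text does not carry the exclusion into 9.6.

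Fourth, the row is pooled, so 5.3% would not appear in it. That stands: the reported row would be off by about 2.2% to 2.6% at full OLE completion.

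Fifth, the general per-period formula that opens 9.6.1 might be meant as the default for subjects who stay in the Main Study only. It is worded by study period, so this is unclear. If it is the default, the same fault applies: 112 days against 98.

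Finally, placebo days are visible in the RWP row and the listings. That is so, but the across-period row is not corrected for them.

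**Conclusion.** The point holds. Followed as written, SAP 9.6 and 9.6.1 report 280 days of JZP-258 exposure for a placebo-arm OLE completer who had 266. That is 5.3% too much for the subject and 2.6% for the two-arm mean. These figures assume nominal period lengths and full OLE completion; a late Visit 16 raises them to 6.4% and 3.1%. The total depends on an OLE uptake that the documents do not give. For rollover subjects the result does not depend on how study drug is read. For re-entry subjects it rests on the term covering placebo, which the operative text of both documents supports.

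The consequence is limited to a descriptive summary. Efficacy results, type I error and event incidence are untouched, and no planned rate uses exposure time. It should be corrected because the reported number would be wrong and the correction is simple.

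**What to change.** In SAP 9.6.1, keep the existing spans and subtract the double-blind dosing span (last minus first double-blind dose date, plus 1) for subjects who received only placebo in the RWP, using the classification already in SAP 5.3. Subtraction is safer than adding up the open-label periods because it does not depend on how a night's dose is dated. For a rollover subject:

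- Bedtime dates: 280 − 14 = 266; summing the periods gives 84 + 14 + 168 = 266.
- Last dose dated after midnight: 281 − 15 = 266; summing the periods gives 85 + 15 + 169 = 269.

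State a formula with the same rule for subjects who take part in the Main Study only. Take the across-period average nightly JZP-258 dose, for which no derivation is given, over the same days. If none of this is adopted, relabel the row as exposure to study drug (JZP-258 or placebo).

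The cost is one or two derivation sentences and no new data. Reported JZP-258 exposure falls slightly.

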3.1.1.2 Optimized Treatment and Titration Period (12 weeks)

During this period subjects will be transitioned to JZP-258 based on their treatment status at study entry. All subjects will begin JZP-258 treatment at the beginning of this period and continue through Week 12. They will be treated with JZP-258 alone for the final two weeks of this 12 week period. Once the JZP-258 dose has been optimized per the Investigator's judgment, these subjects may enter the 2 week Stable-Dose Period with that dose. For the purposes of describing the transition to JZP-258, these subjects' pretreatment status will be defined as Pre-randomization Groups 1-4.

Pre-randomization Group 1

(Subjects on Xyrem at study entry)

Subjects who are only treated with Xyrem as an anticataplectic at study entry will be switched from Xyrem gram for gram to JZP-258 and remain on this JZP-258 dose for a minimum of 2 weeks. If needed, the dose of JZP-258 may then be titrated during the subsequent 8 weeks to a stable, tolerable, and effective dose. Subjects must be maintained on an unchanged, tolerable, and effective dose of JZP-258 for at least 2 weeks prior to entering the Stable-Dose Period.

Pre-randomization Group 2

(Subjects on Xyrem and an additional anticataplectic at study entry)

Subjects who enter the study on Xyrem and an additional anticataplectic will be switched from Xyrem gram for gram to JZP-258 and remain on this JZP-258 dose for a minimum of 2 weeks. Following this 2-week period subjects will be tapered off the additional anticataplectic over a minimum period of 2 weeks and up to 8 weeks. If needed, the dose of JZP-258 may be further titrated to a stable, tolerable, and effective dose during this 8-week period. Subjects must be maintained on an unchanged, tolerable, and effective dose of JZP-258 alone for at least 2 weeks prior to entering the Stable-Dose Period.

Pre-randomization Group 3

(Subjects on a non-Xyrem anticataplectic at study entry)

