Visits 4, 5, 7, 8, 9, and 11

- Record all AEs that occurred since the last visit or phone contact on the AE eCRF.
- Record all concomitant medications that were taken since the last visit or phone contact on the concomitant medications eCRF.
- Administer the PHQ-9 (Weeks 2, and 6 only).
- Discuss the frequency of cataplexy attacks with the subject and confirm that the Cataplexy Frequency Diary is being completed.
- Discuss dosing with the subject and confirm compliance; confirm that the Dosing Diary is being completed.
- Discuss tapering of anticataplectics with the subject (Groups 2 and 3 only).
- Assess control of cataplexy, EDS and tolerability to current dose.
 - All Pre-randomization Groups: If needed, continue titration of JZP-258 and provide instructions for dosing (titration up or down or staying on the current dose) until the next phone contact or clinic visit. JZP-258 dose adjustments are not allowed after Week 10.
 - Pre-randomization Groups 2 and 3: If further JZP-258 titration is not needed and the subject has remained on the same JZP-258 dose for the previous 2 weeks begin taper of the non-indicated anticataplectic.
 - Pre-randomization Groups 2 and 3: When taper of non-Xyrem anticataplectic is initiated, assess taper progress and advise subject on taper instructions, as appropriate.
 Anticataplectic taper must be completed by Week 10.
- Schedule the next phone contact or clinic visit.

CLINIC VISITS - END OF WEEK 4 AND 8 - VISITS 6 AND 10

- Obtain weight in ordinary indoor clothes (without shoes).
- Obtain vital signs (systolic and diastolic blood pressure, heart rate and respiratory rate, and body temperature), in the seated position after the subject has been resting for 5 minutes.
- Obtain a blood sample for electrolytes (Na, K, Ca, and Mg).
- Obtain a urine pregnancy test for all females of childbearing potential (Section 6.10.1).
- Perform alcohol screen and urine drug screen.
- Record all AEs that occurred since the last phone contact on the AE eCRF.
- Record all concomitant medications that were taken since the last phone contact on the concomitant medications eCRF.
- Administer:
 - C-SSRS Since Last Visit version.

Confidential Page 72 of 148

- PHO-9.
- Review Cataplexy Frequency Diary for completeness.
- Review the Dosing Diary for compliance with dosing.
- Assess control of cataplexy, EDS and tolerability to current dose.

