7.1.3 End of Titration Period and Start of Stable-Dose Period

End of Week 12 - Visit 14

- Obtain weight in ordinary indoor clothes (without shoes).
- Obtain vital signs (systolic and diastolic blood pressure, heart rate and respiratory rate, and body temperature), in the seated position after the subject has been resting for 5 minutes.
- Obtain a urine pregnancy test for all females of childbearing potential (Section 6.10.1).
- Obtain a blood sample for electrolytes (Na, K, Ca, and Mg).
- Perform alcohol screen and urine drug screen.
- Administer:
 - C-SSRS Since Last Visit version.
 - PHQ-9.
- Review Cataplexy Frequency Diary for completeness.
- Review the Dosing Diaries for compliance with dosing.
- Record all AEs that occurred since the last visit or phone contact on the AE eCRF (Section 6.13).
- Record all concomitant medications that were taken since the last visit or phone contact on the concomitant medications eCRF.
- Collect any remaining study drug from the Titration Phase and assess compliance.
- Confirm that a stable dose has been reached (i.e., a dose that achieves an optimal clinical benefit with adequate control of cataplexy and EDS while maintaining tolerability) and has remained unchanged for the last 2 weeks of the Optimized Treatment and Titration Period.
- Dispense study drug for the Stable-Dose Phase and provide instruction for how the subject should begin taking study drug on that evening.
- Schedule the next Clinic Visit (Visit 15).

Confidential Page 74 of 148

Clinical Trial Protocol: 15-006 Amendment 5

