The average time to taper off antiepileptic medication will be summarized for Pre-randomization Group 2 and Group 3 subjects combined. For each subject, Time to taper off antiepileptic medication, in days, is the time from the Study Day 1 to one day after the latest end date of the concomitant medication taken as an antiepileptic during the TTP. Antiepileptic medications discontinued prior to Study Day 1 were not included in the summary of time to taper off.

Another table will summarize the number and percentage of subjects on stimulant use during SD and DB RWP periods. The list of stimulant medication will be provided by Jazz.

Past and post medications will be provided in subject data listings only.

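### Time to stable dose is dated at the first night on the eventual dose, which is too early for any subject who leaves that dose and returns to it

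*SAP*

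**What the plan says.** SAP 9.6 lists time to the total nightly stable dose among the exposure summaries for the titration period, overall and by Pre-randomization Group. SAP 9.6.1 gives the derivation. The clock starts at the "date of the first day of the first Open-Label study drug dispensation". It stops at the administration date of the total nightly stable dose "when it was first achieved based on total dose consideration", and one day is added. The population is restricted: "The stable dose determination and time to get to the stable dose will only be calculated for subjects entering the OL SDP".

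The protocol describes stability as a dose that is held. At Visit 14 (Protocol 7.1.3) the site confirms that the dose "has remained unchanged for the last 2 weeks of the Optimized Treatment and Titration Period". Protocol 7.1.2.3 permits "titration up or down or staying on the current dose" and sets the limit: "JZP-258 dose adjustments are not allowed after Week 10".

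A related timing is in SAP 9.5. Time to taper off, for Groups 2 and 3 combined, "is the time from the Study Day 1 to one day after the latest end date" of the tapered agent. On Group 2, Protocol 3.1.1.2 says: "Following this 2-week period subjects will be tapered off the additional anticataplectic over a minimum period of 2 weeks and up to 8 weeks". Group 3 likewise has at least two weeks of initial JZP-258 titration before its taper.

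**The concern.** The SAP rule identifies an amount and looks for the first night that amount was taken. The protocol's idea of a stable dose is an amount that is then kept. The two agree unless a subject passes through the eventual dose, moves away and returns, and the protocol's titration rules allow exactly that.

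The error runs one way. The first night on a dose can never fall after the start of the last continuous run on it, so the rule can only make titration look faster. Subjects converted gram for gram from Xyrem (Groups 1 and 2) are the most exposed. If they end on their conversion dose after a trial of another dose, they score one day however long the trial lasted. At stake is a descriptive account of how long it takes to settle on a dose.

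**Working it through.** **Plan's own figures.** The documents state no expected value for either timing, so there is none to reproduce. The protocol timeline is consistent: 2 weeks before taper + up to 8 weeks of taper or titration + 2 weeks unchanged = 12 weeks, the stated length of the period.

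**Time to stable dose.** Let *F* be the first day on the eventual total nightly dose and *R* the first day of the final continuous run at that dose. With first dispensation and first dose on Day 1, the SAP value is (*F* − 1) + 1 = *F*, and the sustained-dose value is (*R* − 1) + 1 = *R*. The error is *R* − *F*, which is never negative.

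The paths below are assumed. They follow the starting rules and the 1 or 1.5 g weekly steps in Protocol 5.1.1.3 and imply no view on dosing.

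| Assumed path (g/night) | SAP value *F* | Sustained value *R* | *R* − *F* |
|---|---|---|---|
| Converted at 7.5, never changed | 1 | 1 | 0 |
| 4.5, 6, then 7.5 held from Week 3 | 15 | 15 | 0 |
| 4.5, 6, 7.5, then 9 for two weeks, then 7.5 held | 15 | 36 | 21 |
| 7.5 for two weeks, 9 for three weeks, then 7.5 held | 1 | 36 | 35 |
| 7.5 for two weeks, 9 to the end of Week 10, then 7.5 held | 1 | 71 | 70 |

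The last row is the outer limit, with the return to 7.5 g on Day 71 and 14 nights left before the end of Week 12.

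The bias in a group mean is the share of subjects who revisit a dose, times their average *R* − *F*. The documents give neither. On the paths above, each percentage point of subjects affected lowers the mean by 0.01 × 21 = 0.21 day to 0.01 × 70 = 0.70 day.

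**Time to taper off.** The SAP value is (end day + 1) − 1, which equals the end day. Days spent tapering are end day − start day + 1. The earliest compliant start is Day 15.

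| Assumed taper | SAP value | Days tapering | Days before taper |
|---|---|---|---|
| Days 15 to 28 | 28 | 14 | 14 |
| Days 15 to 70 | 70 | 56 | 14 |
| Days 57 to 70 | 70 | 14 | 56 |

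Every compliant value therefore contains at least 14 days before the taper begins. Protocol 7.1.2.3 also ties the start of the taper to two weeks on the same JZP-258 dose, so the interval can be longer.

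**The case against.** The strongest reply on the stable dose is that the error is conditional and the examples are constructed. For titration in one direction the rule is exact, and nothing in the documents says reversals are common. The one-day result needs a subject who starts on the final dose. Group 3 starts at 4.5 g, so it arises there only if 4.5 g is also the final dose. This stands, and it limits the size of the point. It does not rescue the rule, which gives a wrong value on paths the protocol allows. The sponsor may say that first achieved was meant as achieved and then kept. The sentence does not say so, and two programmers could report 1 and 36 for the same subject.

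A second reply concerns the remedy. A literal unbroken run would be reset by a single missed night. Protocol 5.6.1 allows a one-night hold, and Protocol 6.7 accepts compliance on 10 of 14 days in the Stable-Dose Period. This stands, and the fix has to deal with it.

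A reader might go further and infer that the taper clock also starts at the wrong point, so that one conversion timing is biased short and the other long. The documents do not support that. SAP 9.5 fully defines an elapsed time from the start of JZP-258 to being off the other agent, which is a coherent measure of conversion. It is long only against a different quantity, days spent tapering. Protocol 9.12 and SAP 9.10 already plan summaries of titration and duration of the tapered agents for Groups 2, 3 and combined, although without a derivation.

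A reader might also take these timings as the main numbers behind the exploratory objective. No section says so. SAP 9.6 presents time to stable dose as an exposure descriptor across all four groups, while the exploratory analyses use Groups 2 and 3 only.

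**Conclusion.** The stable-dose derivation is wrong as written for one class of subjects: those who reach the eventual dose, leave it and return. Their time to stable dose is too short, by 21 to 70 days on the assumed paths. For all other subjects it is correct. The share affected is not given, so no bias in the reported summary can be stated beyond its direction. The conclusion rests on reading the SAP sentence literally and on the protocol's permission to titrate up or down.

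The taper measure is valid as defined. Its name invites a reader to take it for taper length, so a clearer label is worth having, but this is not an error.

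Both outputs are descriptive. The primary and key secondary analyses, the type I error control and the sample size are unaffected. The point is minor and cheap to correct.

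**What to change.** In SAP 9.6.1, define the stop date as the first date of the final continuous run at the assigned total nightly dose carried into the Stable-Dose Period. State that missed or held nights are not dose changes and do not restart the run. Using the assigned dose, a concept SAP 9.7.1 already relies on for compliance, keeps the date from turning on single nights.

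The cost is one clause plus the missed-night rule, and reprogramming of one variable. The dosing diary runs daily from the start of titration (Protocol 6.7), so no new data are needed. Nothing in dosing or titration changes.

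Optionally, label the SAP 9.5 measure *time from Study Day 1 to anticataplectic-free*. Where a first dose reduction is recorded, report taper duration separately under the summaries already planned in Protocol 9.12 and SAP 9.10. The concomitant-medication form holds total daily dose and dates (Protocol 5.6.2). The added duration would need short rules for agents stopped without a recorded reduction, for more than one agent and for partial dates, so it costs somewhat more than the relabelling.
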